AEs associated with pembrolizumab exposure may represent an immunologic etiology. These immune-related AEs (irAEs) may occur shortly after the first dose or several months after the last dose of pembrolizumab treatment and may affect more than one body system simultaneously. Therefore, early recognition and initiation of treatment is critical to reduce complications. Based on existing clinical study data, most irAEs were reversible and could be managed with interruptions of pembrolizumab, administration of corticosteroids and/or other supportive care. For suspected irAEs, ensure adequate evaluation to confirm etiology or exclude other causes. Additional procedures or tests such as bronchoscopy, endoscopy, skin biopsy may be included as part of the evaluation. Based on the severity of irAEs, withhold or permanently discontinue pembrolizumab and administer corticosteroids. Dose modification and toxicity management guidelines for irAEs associated with pembrolizumab are provided in Table 4.

Table 4. Dose Modification and Management Guidelines for Drug-Related Adverse Events

| General instructions: | | | | |
|---|--|--------------------------------------|---|---|
| 
 1. Corticosteroid taper should be initiated upon AE improving to Grade 1 or less and continue to taper over at least 4 weeks. 2. For situations where pembrolizumab has been withheld, pembrolizumab can be resumed after AE has been reduced to Grade 1 or 0 and corticosteroid has been tapered. Pembrolizumab should be permanently discontinued if AE does not resolve within 12 weeks of last dose or corticosteroids cannot be reduced to ≤ 10 mg prednisone or equivalent per day within 12 weeks. 3. For severe and life-threatening irAEs, IV corticosteroid should be initiated first followed by oral steroid. Other immunosuppressive treatment should be initiated if irAEs cannot be controlled by corticosteroids. | | | | |
| irAEs | Toxicity grade or conditions (NCI CTCAE v4.0) | Action taken to pembrolizumab | irAE management with corticosteroid and/or other therapies | Monitor and follow-up |

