5.0 Trial Schedule

The trial will consist of the following three periods:

Screening (SCN) Period: The screening period will take place only after informed consent is obtained and within the 21 days prior to C1/D1. The screening visit may be counted as the baseline visit if completed within 7 days of initial dosing on C1/D1.

Treatment Period: Patients will be treated at 21 ± 3 day intervals. Patient must begin cycle 1 within 21 days of signing the IRB approved informed consent document and after the screening assessments have been performed and reports have been reviewed to confirm eligibility. The patient will continue on maintenance therapy until there is evidence of clear-cut tumor progression, has treatment ending toxicities, or withdraws from treatment (refer to section 4.8). Table 7 below summarizes the Screen-Treatment Period Schedule.

Post Treatment Period: Patients will return to the investigative site for an End of Treatment (EOT) visit within 5 days after the last dose of trial treatment or before the initiation of a new anti-cancer treatment, whichever comes first (refer to Section 6.1.7.3). An additional mandatory Safety Follow-up visit should be conducted approximately 30 days after the last dose of trial treatment and before initiation of a new anti-cancer treatment, whichever comes first (6.1.7.4). WOCBP will be required to have a pregnancy test at this visit.

After the 30 day-FU visit, patients will then move into the Survival Phase and be contacted by telephone every 90 days thereafter until death, withdrawal of consent, or the end of the trial, whichever occurs first. The protocol approved contraceptive guidance (Section 4.7.2) must be followed for at least 120 days (for males) and 180 days (for WOCBP) after the last dose of trial treatment. Table 8 below summarizes the Post Treatment Period Schedule.

Footnotes for Table 7. Screen – Trial Treatment Period Schedule

- a. Written IRB-approved informed consent must be obtained prior to any screening assessments being performed.
- b. Documented medical history to include, demographics, concurrent baseline conditions (using NCI-CTCAE V4. Appendix 3), prior cancer treatment and surgeries.

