- r. For only those patients consenting to the optional tumor biopsy, a baseline tumor biopsy will be collected and used for profiling. If possible (patient condition permitting) this will be repeated after 9 ± 1 weeks on trial treatment, or at the time of disease progression. (Refer to 6.1.2.8).

Table 8. Post-Treatment Period (EOT– Follow-Up) Schedule

| Post-Treatment Period | Scheduling Window (Days) | | |
|--|--|----------------------|---|
| | EOT | 30 days from EOT | Every 90 days post EOT |
| | At time of discontinuation (within 5 days of last dose) | 30 ± 5 days from EOT | 90 ± 5 days from EOT then every 90 ± 15 days ⁱ |
| Post-trial anticancer treatment status | X | X | X |
| Disease/Survival Status ^a | X | X | X |
| Concomitant Medication Review | X | X | X |
| Assess & Report Adverse Events ^b | X | X | X |
| Directed Physical Examination | X | | |
| Patient Personalized Clinical Benefit App | X | | |
| Vital Signs and Weight ^c | X | | |
| ECG | X | | |
| ECOG (see appendix 4) | X | | |
| Serum β HCG Pregnancy Test for WOCBP | X | X | |
| CBC with Differential | X | | |
| Comprehensive Serum Chemistry Panel | X | | |
| Urinalysis | X | | |
| T3, FT4 and TSH | X | | |
| Tumor Imaging ^d | X | | |
| CA19-9 ^e | X | | |
| Central Lab Samples (Blood and Fecal Swab ^f) | X | X ^f | |
| Review contraception use as required by protocol Section 4.7.2 (where applicable) ^g | X | X | X |
| Optional -Tumor Tissue Collection | [Tumor tissue collection for those that consent to this optional collection and undergo a routine care biopsy of their tumor during their participation in the study] ^j | | |
| Contact Information Review ^h | X | X | X |

Footnotes for Table 8. Post –Treatment Period

a. Post-treatment follow-up for disease status until documented disease progression, initiating a non-trial cancer treatment, withdrawing consent or becoming lost to follow-up. After documented disease progression each pt will be followed by telephone for survival status.

b. Assess and record any new or ongoing AEs at time of EOT. Following the EOT, each patient will be followed for 30 days, for adverse event monitoring. Serious adverse events and Events of Clinical Interest (ECI) will be collected for 90 days after the end of treatment as described in Section 6.2.3.1.

c. Vital signs to include: Blood pressure, pulse, respiratory rate, and temperature.

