Fecal samples will be collected by the patient at home during trial participation. Patients will be asked to collect two samples per treatment cycle. One fecal swab sample is to be collected within the 72 hours prior to Day 1 of each treatment cycle, and a second fecal swab sample within 24-72 hours after treatment on Day 1. The patient will also be asked to collect one final sample approximately 30 days following treatment discontinuation. Patients will be provided with collection instructions (refer to Appendix 9), collection container, sterile CultureSwabs in individual pre-labeled containers, and a biospecimen bag. Patients will collect fecal material in a collection container, and then transfer a pea size amount of fecal matter using the provided CultureSwabs, into the original pre-labeled fecal swab collection container, and place in the provided biospecimen bag. The patient will be asked to store the fecal samples in the freezer and deliver to the research site within 72 hours of collection (this will correspond with the patients' return to clinic - so it is not anticipated that additional clinic visits should be required).

6.1.6.1 *Withdrawal/Discontinuation*

When a patient discontinues/withdraws prior to trial completion, all applicable activities scheduled for the EOT visit should be performed at the time of discontinuation. Any adverse events which are present at the time of discontinuation/withdrawal should be followed in accordance with the safety requirements outlined in Section 6.2 - Assessing and Recording Adverse Events.

6.1.6.2 *Blinding/Unblinding*

This is a double-blind, randomized, placebo-controlled phase II trial with the identity of the treatment unknown to the patients, investigators and the Sponsor. Only the site pharmacist and unblinded trial monitor will be aware of the assigned treatment arm.

Investigators will be able to unblind in emergency situations when the identity of the treatment must be known in order to provide appropriate treatment. The sponsor must be contacted (if possible) prior to the treating investigator unblinding a patient.

Additionally, at the time of disease progression the treating investigator may request the unblinded treatment assignment for the patient. This will be provided by the unblinded trial monitor to the treating Investigator for the purposes of considering future treatment options. The remainder of the trial team will not have access to this unblinded treatment assignment.

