6.1.7.3 End of Treatment (EOT)

The patient will continue on maintenance therapy until there is evidence of clear-cut tumor progression, has treatment ending toxicities, or withdraws from treatment (refer to section 4.8). The following assessments will be performed within 5 days after completing the last dose of trial medication or before the initiation of a new anti-cancer treatment, whichever comes first:

- Directed physical exam
- ECOG Performance Status (see Appendix 4)
- Vital signs
- ECG
- Hematology: CBC with differential and platelet count
- Serum chemistries
- TSH, T3, T4
- CA19-9 (or CEA or CA-125 if not expressers of CA19-9)
- Urinalysis
- Serum β -HCG pregnancy test (for WOCBP)
- Central lab blood sample, 2 X10 mL vials
- Concomitant medication
- Patient to complete the PPCB App (Appendix 6)

- Provide Fecal Swab collection kit and review instructions (Appendix 9) with patient for return of sample within 72 hours of collection (coordinate with 30 day Safety Follow-Up visit)
- CT/MRI scan to evaluate disease status (using same imaging method as Baseline). Obtain De-identified dicomm encoded CT scan for central lab (Appendix 7).
- AEs using the NCI CTCAE Version 4.0 (see Appendix 3)
- Review contraception use as required by protocol Section 4.7.2 (where applicable)
- Confirm contact information for patient and a designated family member and remind patient of FU telephone contact that will be conducted every 90 days for survival status following the 30 - day follow-up visit.

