6.1.7.4 Follow-up Period

30-day Follow-up Visit

The mandatory Safety Follow-up visit should be conducted approximately 30 (\pm 5 days) after the last dose of trial treatment and before initiation of a new anti-cancer treatment, whichever comes first.

The following assessments will be performed:

- Serum β -HCG pregnancy test (for WOCBP)
- AEs using the NCI CTCAE Version 4.0 (see Appendix 3)
- Review contraception use as required by protocol Section 4.7.2 (where applicable)
- Confirm contact information for patient and a designated family member and remind patient of FU telephone contact that will be conducted every 90 days for survival status.

All AEs that occur prior to the Safety Follow-Up Visit should be recorded. Patients with an AE of Grade > 1 will be followed until the resolution of the AE to Grade 0-1 or until the beginning of a new anti-cancer therapy, whichever occurs first.

SAEs that occur within 90 days of the end of trial treatment or before initiation of a new anti-cancer treatment should also be followed and recorded.

Survival Follow-up Phase

Once a patient experiences confirmed disease progression or starts a new anti-cancer therapy, the patient moves into the Survival Follow-up Phase and should be contacted by telephone 90 (\pm 5 days) from EOT and every 90 \pm 15 days after that until death, withdrawal of consent, or the end of the trial, whichever occurs first.

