5 ENDPOINTS AND COVARIATES

Primary endpoint: Percent of patients with radiographic disease progression according to RECIST 1.1 at 6 months, defined as 180 days from initial treatment (C1/D1).

Secondary endpoints:

- (1) Incidence of toxicities
From initial treatment to end-of-treatment
- (2) Overall survival
Time from initial treatment to death

Exploratory endpoints:

- (1) Disease progression according to RECIST 1.1 versus iRECIST criteria
Percent of patients with radiographic disease progression at 6 months

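### End of treatment has no single reference date: the EOT visit and safety windows run from the last dose in some sections and from discontinuation or EOT in others, and SAP 5 stops toxicity at that undefined date

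*Protocol*

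**What the plan says.** **EOT visit.** Protocol 6.1.7.3 schedules the EOT assessments "within 5 days after completing the last dose of trial medication", and 5.0 likewise asks for a "visit within 5 days after the last dose of trial treatment". In both, a new anti-cancer treatment brings the visit forward. Section 6.1.6.1 says that "all applicable activities scheduled for the EOT visit should be performed at the time of discontinuation", and 4.8 also speaks of the EOT visit at discontinuation or withdrawal. The EOT column of Table 8 combines the two: "At time of discontinuation (within 5 days of last dose").

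**30-day safety visit.** Section 6.1.7.4 times it about 30 (± 5) days "after the last dose of trial treatment and before initiation of a new anti-cancer treatment, whichever comes first", and 5.0 agrees. Table 8 times it 30 ± 5 days from EOT.

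**AE and SAE windows.** Table 8 footnote b states: "Following the EOT, each patient will be followed for 30 days, for adverse event monitoring", with SAEs and ECIs collected for 90 days after the end of treatment. Table 7 footnote c also counts from EOT. Section 4.8 counts from the end of treatment. Sections 6.2, 6.2.3.1 and 6.2.3.2 count from cessation of treatment. None of these terms is defined.

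**Holds.** The general instructions to Table 4 (4.2.4) state: "Pembrolizumab should be permanently discontinued if AE does not resolve within 12 weeks of last dose". Section 4.2.5 holds paricalcitol for an AE attributable to paricalcitol. No section says whether paricalcitol or placebo continues while pembrolizumab is withheld.

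**Analysis.** SAP 5 defines the toxicity endpoint as "From initial treatment to end-of-treatment". SAP 7.1 and protocol 8.3.5.1 summarise all AEs on or after C1/D1 and give no end date.

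**The concern.** The two ways of dating EOT agree only when dosing runs up to the decision to stop. When treatment is on hold and the hold becomes permanent, nobody knows that the last dose was the last until later. By then the 5-day EOT window may have closed, and part or all of the 30-day window may have run out. One site could date EOT from the last dose and another from the decision, and both would be following the protocol.

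Toxicity is the first secondary endpoint, and proposed SAP Table 3 compares events of grade 3 or higher between arms with P values. Protocol 6.2.4 has every grade change recorded. An event that worsens to grade 3 during a hold would therefore count under one EOT date and not under the other. With 12 patients per arm, one patient is 1/12 = 8.3 percentage points.

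The SAP 5 cut-off is a problem even without a hold. Read literally, it drops from every patient the AEs that the protocol collects in the 30 days after EOT and the SAEs and ECIs that it collects in the 90 days after EOT. The EOT blood sample (6.1.2.7) and the EOT symptom score (8.3.6.3) move with the same date.

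**Working it through.** No stated figure in the plan has to be reproduced. The check is calendar arithmetic on the protocol's own windows.

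**Inputs.** Day 0 is the last dose of trial treatment, and h is the number of days from then to the decision to discontinue. The EOT visit is allowed 5 days (5.0, 6.1.7.3), the safety visit is at 30 ± 5 days (6.1.7.4, Table 8), AE collection lasts 30 days and SAE/ECI collection 90 days (Table 8 footnote b, 6.2). The longest stated pembrolizumab hold is 12 weeks from the last dose: 12 × 7 = 84 days (Table 4).

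**Formulas.** Gap between the two reference dates = h. The Table 8 cell can be met only if h ≤ 5.

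| Item | Counted from last dose | Counted from discontinuation/EOT | At h = 84 |
|---|---|---|---|
| EOT visit | by day 5 | day h | by day 5 or day 84 (79 to 84 days apart) |
| 30-day visit | days 25 to 35 | days h + 25 to h + 35 | days 25 to 35 or 109 to 119 |
| AE window ends | day 30 | day h + 30 | day 30 or 114 |
| SAE/ECI window ends | day 90 | day h + 90 | day 90 or 174 |

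If the decision falls on day 84, the last-dose reading has closed the EOT window 84 − 5 = 79 days earlier and the AE window 84 − 30 = 54 days earlier. It leaves 90 − 84 = 6 days of SAE/ECI collection.

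**When h reaches 84.** The 12-week limit is a pembrolizumab rule. Taking the last dose to be the last of either drug, h = 84 requires paricalcitol or placebo to be held for the same time. If it continues, the last dose is recent: dosing on days 1, 3, 5, 8, 10, 12, 15, 17 and 19 of a 21-day cycle leaves 2 or 3 days between doses (before the ± 1 day allowance), so the gap is a few days. The protocol settles neither whether the second drug continues nor which drug's last dose is meant.

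**What the gap exposes.** Several rules do not depend on the EOT date. SAEs judged related to pembrolizumab are reportable at any time, and all SAEs are followed for outcome (6.2.3.1). AEs above Grade 1 are followed to Grade 0-1 or the start of new anti-cancer therapy (6.1.7.4). What remains exposed is mainly new non-serious AEs, SAEs judged unrelated, and grade changes after whichever EOT date is chosen.

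**SAP 5 against SAP 7.1.** SAP 5 closes the endpoint at end of treatment; SAP 7.1 and protocol 8.3.5.1 do not close it. Both cannot be followed. The open-ended text is still bounded by what is collected, and the end of collection depends on the undefined date.

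**The case against.** The strongest case on the other side is that this is loose wording with little effect. Its points differ in strength.

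- **Size.** A reader might infer that the windows differ by 12 weeks for patients stopped after a hold. The documents do not support that without a condition. The limit applies to pembrolizumab alone, and no text says that both drugs stop together. This point stands.
- **Other holds.** A reader might add paricalcitol holds (4.2.5), or 4 to 6 weeks (28 to 42 days) awaiting a repeat scan (6.1.2.6). Section 4.2.5 says nothing about discontinuation. Section 6.1.2.6 lets clinically stable patients continue and does not describe a hold for the others. Several Grade 3 or 4 events in Table 4 go straight to permanent discontinuation. This stands too: only the pembrolizumab route clearly describes a hold that becomes permanent.
- **Toxicity analysis.** SAP 7.1 drops no recorded event, and the event that prompted a hold would normally have begun around the last dose and so count on either date. This is true of SAP 7.1, but SAP 5 says otherwise and nothing ranks one over the other.
- **Safety follow-up.** It is largely protected, as shown above, so a claim that the course of immune-related toxicity would go unrecorded goes too far. This stands.
- **Natural reading.** Cessation of treatment would not normally mean the start of a temporary hold. That helps with 6.2, but not with the explicit last-dose wording in 5.0, 6.1.7.3 and 6.1.7.4, or with the Table 8 cell.

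The primary endpoint is untouched, and the symptom comparison is exploratory. The objection limits the size of the problem; it does not remove the contradiction.

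**Conclusion.** Wrong as written, in two places. First, the protocol gives the EOT visit and the 30-day safety visit two reference dates each and leaves the AE and SAE windows on undefined terms. The Table 8 cell cannot be met when discontinuation comes more than 5 days after the last dose. Second, SAP 5 conflicts with SAP 7.1, with protocol 8.3.5.1 and with the 30-day and 90-day collection periods, whether or not there was a hold.

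The first problem is as large as the hold is long. It reaches 84 days on the assumption that both drugs are held for the full 12 weeks and that no new anti-cancer treatment starts meanwhile, and it is a few days if paricalcitol or placebo continues. The documents give no basis for the number of such patients, so none is offered. The consequence falls on the secondary toxicity endpoint and on post-treatment collection, mainly new non-serious AEs, unrelated SAEs and later grade changes. It does not reach the primary endpoint.

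**What to change.** - **Protocol.** Reconcile 4.8, 5.0, Tables 7 and 8, 6.1.6.1, 6.1.7.3, 6.1.7.4 and 6.2 to one defined EOT reference date that can be met when a hold becomes permanent. State whether the last dose means that of either drug or of both, and use one term in place of EOT, end of treatment and cessation of treatment.
- **SAP 5.** Bring it into line with SAP 7.1: toxicity covers all AEs from C1/D1 through the end of the protocol collection window, counted from that one date. The window is 30 days for AEs and 90 days for SAEs and ECIs, with the shortening already stated for new anti-cancer therapy.

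The cost is wording in a routine amendment and one line in the SAP. The small downside is that AEs may be recorded for slightly longer in a few patients. No rule on when treatment is held or stopped is changed, and no view is taken on those rules.

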6.1.7.4 Follow-up Period

30-day Follow-up Visit

The mandatory Safety Follow-up visit should be conducted approximately 30 (\pm 5 days) after the last dose of trial treatment and before initiation of a new anti-cancer treatment, whichever comes first.

The following assessments will be performed:

- Serum β -HCG pregnancy test (for WOCBP)
- AEs using the NCI CTCAE Version 4.0 (see Appendix 3)
- Review contraception use as required by protocol Section 4.7.2 (where applicable)
- Confirm contact information for patient and a designated family member and remind patient of FU telephone contact that will be conducted every 90 days for survival status.

All AEs that occur prior to the Safety Follow-Up Visit should be recorded. Patients with an AE of Grade > 1 will be followed until the resolution of the AE to Grade 0-1 or until the beginning of a new anti-cancer therapy, whichever occurs first.

SAEs that occur within 90 days of the end of trial treatment or before initiation of a new anti-cancer treatment should also be followed and recorded.

Survival Follow-up Phase

Once a patient experiences confirmed disease progression or starts a new anti-cancer therapy, the patient moves into the Survival Follow-up Phase and should be contacted by telephone 90 (\pm 5 days) from EOT and every 90 \pm 15 days after that until death, withdrawal of consent, or the end of the trial, whichever occurs first.

6.2 Assessing and Recording Adverse Events

An adverse event is defined as any untoward medical occurrence in a patient or clinical investigation patient administered a pharmaceutical product and which does not necessarily have to have a causal relationship with this treatment. An adverse event can therefore be any unfavorable and unintended sign (including an abnormal laboratory finding, for example), symptom, or disease temporally associated with the use of a medicinal product or protocol-specified procedure, whether or not considered related to the medicinal product or protocol-specified procedure. Any worsening (i.e., any clinically significant adverse change in frequency and/or intensity) of a preexisting condition that is temporally associated with the use of the pembrolizumab and /or paricalcitol, is also an adverse event.

Adverse events may occur during the course of the use of pembrolizumab and/or paricalcitol in clinical trials, or as prescribed in clinical practice, from overdose (whether accidental or intentional), from abuse and from withdrawal.

Progression of the cancer under study (pancreatic cancer) is not considered an adverse event.

All adverse events that occur after the consent form is signed but before treatment allocation/randomization must be reported by the investigator if they cause the patient to be excluded from the trial, or are the result of a protocol-specified intervention, including but not limited to washout or discontinuation of usual therapy, diet, placebo treatment or a procedure.

From the time of treatment allocation/randomization through 30 days following cessation of treatment, all adverse events must be reported by the investigator. Such events will be recorded at each examination on the Adverse Event case report forms/worksheets. The reporting timeframe for adverse events meeting any serious criteria is described in section 6.2.3.1. The investigator will make every attempt to follow all patients with non-serious adverse events for outcome.

